Evaluation Materials	
Evaluation Tools comprising main measures for study endpoints made available electronically include:
 
 ○ Subjective self- assessment scales (clinically standardised: SSQ and HUI Mk III); ○ Patient profile forms (clinician and recipient questionnaire versions); ○ Hearing threshold measures (routine measures performed at the clinic) ○ Product specific evaluations as required
Inclusion criteria:	
 ○ Post-lingually deafened adults and adolescents who are newly implanted AND prior to first switch-on of their external device. ○ Unilateral, bilateral simultaneous recipients of any implant device(s) available with market approval from the company Cochlear®. ○ Children 10 years or older, and in accordance with local regulations and product labelling. ○ Mentally capable to respond to self-administered assessment scales ○ Willingness to participate and sign the Patient Informed Consent (PIC) form directly or signed by the legal representative. 
NOTE: Unilateral implant-users registered at baseline, electing to opt for a second sequential implant during the course of the 3 year follow-up period shall be re-classified accordingly there-after as sequentially bilaterally implanted.

Exclusion Criteria	
 Individuals excluded from participation in a registry according to national or local regulations. 							
Primary Objectives:	To evaluate longitudinal subjective benefit data using validated standardised questionnaires (HUI Mk3 and SSQ) for prospectively implanted adult and adolescent recipients compared to the preimplant condition. To assess daily use and issues reported through Cochlear's complaints and issues handling procedure.							
Secondary Objectives:	
To provide statistically valid data to support patient management decisions at the clinical, administrative, reimbursement and regulatory levels locally, nationally and internationally.
 
To establish benefits and device functionality for bilateral use over unilateral use for scientific, regulatory and market-oriented communications.
							
Evaluation Plan	Evaluations are performed at the Baseline interval (post-implant and pre-switch-on) with annual follow-up at 1 year, 2 years (and optionally at 3 years) post-implant. Clinicians and recipients are strongly encouraged to use all evaluation tools below.							
			Test interval	Baseline	Follow-up			Comments

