- Inter-group comparisons of outcome data require ideally a minimum of 50-100 subjects per subgroup per device type and configuration (and of comparable age group) for data analysis and formal report of their SSQ data at the 1st, 2nd and 3rd year post-implant compared to their preoperative baseline responses. Analysis will performed via comparison of mean responses per subcategory scale of questions of the SSQ as proposed by the developers. Sub scale category scores will be compared across time both intra-subject and inter-subject using parametric tests of comparison.
- Data gathered from the general questionnaires will be collated to provide a descriptive report of patient characteristics of the enrolled population.

- Hearing threshold data for pure-tone stimuli under headphones for air-conduction and via a bone conductor for bone-conduction may also be recorded by the clinician following routine measurements at the clinic at the 1st, 2nd and 3rd year post-implant compared to their preoperative baseline responses. Test data collected at one additional time interval post-implant immediately post-surgery and prior to switch-on may also be entered and collated. Threshold data specifically for air-conduction measures per frequency per subject will be compared to determine the changes in threshold over time for each ear. Changes of +/-5 dB will be considered clinically insignificant. Changes in thresholds per frequency will be reported intra-subject and for inter-subject groups.
- Other evaluation measures such as speech audiometry are not specified for longitudinal data collection by the protocol. However additional clinic specific data may be recorded by each clinic on the hearing threshold summary forms provided for the same group of subjects for both formal internal and external reports.
- Participating clinics and or patients wishing to complete the questionnaires online will be required to confirm the minimum technical PC requirements and firewall conditions. (See Section 13).
- Product-specific measures (e.g. surgical experience, in situ thresholds).

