- **Clinician Baseline – Compulsory**, this form must be completed by the clinician with reference to each newly enrolled patient as it serves as registration of the patient at baseline evaluation. This is to ensure capture of the specific information related to technical details of the implanted device or devices and the external devices to be used, as well as any specific clinical technical details the patient does not have access to.
- **Annual Follow-up- Clinician (post implant: 1yr and 2yrs compulsory (and 3yrs optional))**. This is a general questionnaire that must be completed at an annual follow-up evaluation which coincides with routine annual clinic visit for the patient. This is to ensure capture of the specific information related to technical details of the implanted device or devices and the external

devices, and to reflect any changes that may have occurred over the preceding 12 months. Again it refers only to specific clinical technical details the patient does not have access to.

- **Product Specific procedures.**
- **End of study form** is also a compulsory form required to be completed by the clinician for each registered patient upon their departure from the registry either at the end of the prescribed set of evaluations, that is at 2 years or optionally 3 years post-implant or prematurely. A patient or clinician may choose to terminate participation in the registry prematurely at the individual wish of the patient or clinician or alternative following an event requiring removal of the patient from further review and data collection by the registry by default. The clinician is asked to record the reason for removal and date of exit from the study for each patient.
- **Unaided Hearing Threshold summaries.** The hearing threshold summary data recorded at baseline must reflect measurements performed prior to the implant surgery. Additionally, hearing thresholds measured immediately after surgery, in the period between surgery and before 1st switch-on or later) can be recorded at baseline evaluation. The evaluation form aims to capture a detailed summary of the pure tone hearing threshold levels that are routinely measured for the patient.
 1. **Pre-implanted hearing thresholds** routinely measured prior to the patients surgical procedure, for pure-tone stimuli via air and bone conduction in each ear for routinely measured frequencies between 125Hz and 8000 Hz) are required.

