13.2 Data Reporting

Evaluation case report forms to standardly gather general patient demographic data, and responses to the clinically standardised self-assessment scales, the SSQ and HUI MARK III, as well as audiometric data sheets (and product-specific measures), are provided as printable forms through the electronic user interface accessed via the allocated user password. The interface to the data sheets is designed for direct data-entry online with same time updates. Entered data is captured electronically into a central externally hosted e-platform developed, hosted and maintained by [REDACTED], as contracted database consultants for the company Cochlear, operating to ISO standards for data protection and data management. The project manager and select regional Cochlear staff will have access to view all raw data and data summaries. Clinics have ready access to all data entered related to their patients registered at their clinic via same time update summaries and through use of the system allocated confidential user password (delivered to each investigator by email). Subsequent automated email-reminders for patient reviews will also be provided through the e-platform as provided by the registering Clinician to alert for timely annual reviews of registered patients.

Specific instructions to complete the electronic evaluation forms shall be provided to the clinic investigator and other site personnel and registered patients online and reviewed during the initiation into the observational study onsite by Cochlear clinical staff.

Data entry at Baseline

Upon registration of the patient into the Observational study at baseline via the responsible clinician, the patient code will be automatically assigned via the platform according to the scheme outlined under the section entitled *Subject Identification and Confidentiality* of this protocol. During registration of the patient and completion of the *Clinician Baseline-Compulsory form*, the clinician and patient will agree upon which further assessments shall be included at baseline for the patient in question. The additional evaluation tools to select from include: Implant Recipient Baseline form, HUI Mark III and the SSQ and hearing threshold summaries and product specific evaluation measures.

Paper response options for the patient

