14.2 Sponsor

Cochlear, the sponsor will use this data to provide statistically valid data to support patient management decisions at the clinical, administrative, marketing, reimbursement and regulatory levels locally, nationally and internationally. Reports are to be developed at regular intervals back to the contributing clinics and at request of the relevant health and government bodies. Established benefits will be used to support benefit claims from use of bilateral stimulation over unilateral stimulation for scientific, regulatory and market oriented communications.

The study obligations for the Sponsor and the investigator are followed as outlined in guidelines for ISO14155 and the Declaration of Helsinki. These will be reviewed with the clinician prior to the start of the registry at initiation visit.

15 Withdrawal of Sponsor

Following written communication to notify in advance all participating collaborating clinics, the sponsor may elect to withdraw sponsorship of the registry if,

- patient recruitment rate is not growing sufficiently over time to warrant the support of resources involved..
- there is no willingness to collaborate in the registry by the clinicians on the whole.

Note: In the event the registry is closed, patients enrolled to this date would be permitted to complete evaluation to 2 years post-implant

16 Overview of Case Report Forms and Questionnaires available online

Baseline evaluation

By the patient
 Implant Recipient Baseline
 HUI Mark III questionnaire
 Speech Spatial Qualities questionnaire
By the Clinician

Clinician Baseline (compulsory)
Unaided Hearing threshold summary- pre-implant
Unaided Hearing thresholds - immediately post implant
End of study form (if needed)
Product specific forms

1st year follow up

By the patient
Implant Recipient follow-up
HUI Mark III questionnaire
Speech Spatial Qualities questionnaire
By the Clinician
Annual Follow-Up Clinician Yr 1 (compulsory)
Unaided Hearing Thresholds - Yr 1
End of study form (as needed)
Product specific forms

2nd year follow up

By the patient
Implant Recipient follow-up form
HUI Mark III questionnaire
Speech Spatial Qualities questionnaire
By the Clinician
Annual Follow-Up Clinician Yr 2 (compulsory)
Unaided Hearing Thresholds -Yr 2
End of study form (as needed)
Product specific forms

3rd year follow up (optional)

By the patient
Implant Recipient follow-up form
HUI Mark III questionnaire
Speech Spatial Qualities questionnaire
By the Clinician

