**2.3 Statistics****2.3.1 Sample Size**

There are a total of 1361 baseline records available in the IROS database, with 1192 with some exploitable threshold data (BC value or HL degree category missing for 50 Baha and 115 CI). There are approximately 247 of the total set with BC data, of which 84 are CI. Thus, most of the CI group have HL degree but no specific AC or BC data. The exploitable AC and BC data will be used to provide individual data points. The HL degree data for CI can be summarised in terms of a range of values.

It is known that BC thresholds above ~80 dB HL cannot be measured due to transducer saturation. When this occurs often an AC threshold alone is given, but these are generally of high values.

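### Pre-implant thresholds are mandatory in Protocol 6.1.3 but selectable in 13.2, and the SAP's sensorineural/conductive plot rests on the 18% of records with bone-conduction data

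*Protocol*

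**What the plan says.** **Protocol.** Section 6.1.3 describes the unaided threshold summary. Pre-implant AC and BC values "in each ear for routinely measured frequencies between 125Hz and 8000 Hz) are required". The next item, thresholds immediately after implantation, is left to the clinic's discretion.

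Section 13.2 says of baseline registration that "the clinician and patient will agree upon which further assessments shall be included at baseline for the patient in question". It continues: "The additional evaluation tools to select from include: Implant Recipient Baseline form, HUI Mark III and the SSQ and hearing threshold summaries". In section 16 the only baseline form with a compulsory mark is "Clinician Baseline (compulsory"); the pre-implant threshold form has none. The synopsis says of the whole set of tools: "Clinicians and recipients are strongly encouraged to use all evaluation tools below".

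Section 6 says threshold data "may also be recorded by the clinician following routine measurements at the clinic", in a sentence about the annual follow-up measures. Section 6.2.2 makes the hearing summaries part of the secondary end-points.

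**SAP section 2.** The device-profile paper uses all available baseline data and plans no formal tests. Section 2.1 takes BC as the sensorineural (SN) component and AC minus BC as the conductive (CO) component. Section 2.3.2.2 addresses its hypothesis by plotting ipsilateral SN and CO values on a schema of device ranges. Section 2.3.1 gives the record counts and adds: "Thus, most of the CI group have HL degree but no specific AC or BC data". The remaining CI records are to be summarised as a range from their degree category. The same section notes that BC above about 80 dB HL cannot be measured, and that often only an AC value is then given.

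**The concern.** A clinic reading 6.1.3 would conclude that it must enter the pre-implant audiogram. A clinic reading 13.2 or 16 would conclude that it may leave it out. The Protocol does not say which section governs.

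The SN/CO plot needs BC for the SN component, and both AC and BC for the CO component. A degree category cannot separate the two. If the CI records with BC differ from those without, the plotted CI cloud shows which records could be plotted as well as what CI recipients are like. A reader of the publication would take it as the CI profile. SAP section 2 plans no check on this: the text on comparing records with and without data is in section 1 and concerns follow-up in the age paper.

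**Working it through.** **Inputs, all from SAP 2.3.1.** Baseline records 1361. Records with some exploitable threshold data 1192. Records with BC value or degree category missing: 50 Baha and 115 CI. Records with BC data about 247, of which 84 are CI. The total number of CI records is not stated.

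**1. The SAP's own figure.** 1361 − 50 − 115 = 1196, against the stated 1192. Put the other way, 1361 − 1192 = 169, against 50 + 115 = 165. The four records (0.3%) are not assigned to a device group. They may belong to groups the sentence does not itemise, so this is a gap in the account and not a demonstrated error.

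**2. What enters the paper.** Some exploitable data: 1192/1361 = 87.6%. BC data: 247/1361 = 18.1% of all records, or 247/1192 = 20.7% of exploitable ones. Exploitable without BC: 1192 − 247 = 945, or 69.4% of all records. The 247 is a ceiling for paired AC and BC, because the number with both is not given.

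**3. The CI share, bounded because the denominator is missing.** Assume the 115 are CI records with neither BC nor degree.
- Smallest CI total: 84 + 115 = 199, so the share with BC is at most 84/199 = 42.2%.
- Largest CI total: remove the 247 − 84 = 163 non-CI records with BC, the 50 Baha records and the four unassigned ones. 1361 − 163 − 50 − 4 = 1144, so the share is at least 84/1144 = 7.3%.
- The SAP says most CI records have degree only. Then N − 84 − 115 > N/2, so N > 398 and the share is below 84/398 = 21.1%.

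Without the assumption about the 115, the SAP's word for a majority still gives N > 2 × 84 = 168 and a share below 50%. Most CI records lack BC on any of these readings.

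**4. Direction.** If BC above a limit L (about 80 dB HL) cannot be recorded and such records drop out of the plot, the remaining points have SN ≤ L. Omission for this reason removes the poorest BC values and shifts the CI points toward better BC. The effect of unentered forms has no known direction.

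**5. What a censored record still shows.** If BC is known to exceed L, then SN > L and CO < AC − L. With a recorded AC, the record gives a bounded point and need not be dropped.

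**The case against.** Several points on the other side stand.

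- **Reading of 6.1.3.** It can be taken to say which measurement the form must hold (pre-surgical), and not that every patient must have a form. Other forms in that section carry an explicit compulsory label and this one does not. But the contrast with the discretionary next item favours an obligation, and the need for two readings is itself the problem.
- **Section 6.** Its permissive wording attaches to the annual measures. It does not make the pre-implant measure optional; the contradiction rests on 13.2 and 16.
- **Routine measures only.** Section 6.1.3 covers frequencies that are routinely measured, so a record without BC is not by itself a breach.
- **Limited consequence.** The paper is descriptive, thresholds are secondary, and no HUI3 or SSQ analysis is touched.
- **Existing data.** A compulsory form does not change records already collected, and BC beyond the transducer limit cannot be entered later.

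A reader might infer that the whole device-profile paper describes a self-selected minority. The documents do not support this: 87.6% of records contribute something, and the SAP gives a measurement ceiling as one reason for absent BC. That ceiling is not an obvious full explanation either, since the SAP says AC is then often given, yet most CI records have no specific AC value. The documents do not apportion the two causes.

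A reader might also take the 82% without BC as evidence that threshold change over time cannot be computed. Section 6 plans that comparison specifically on AC. The SAP gives neither a count of AC-only records nor any follow-up counts, and its hearing-preservation section is currently not applicable.

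**Conclusion.** The point holds in a limited form. The Protocol contradicts itself on whether the pre-implant threshold form must be entered, most clearly between 6.1.3 and 13.2, with section 16 in support. The individual SN/CO plot, which addresses the SAP section 2 hypothesis, can use at most about 247 of 1361 records (18%). For CI it can use 84 of an unstated total: below about 21% if the SAP's statement about most CI records is taken with the reading of the 115 given above, and between 7.3% and 42.2% on that reading alone.

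The subset is selected by entry and by measurability, in unknown proportions. That the CI points lean toward better BC is probable and not demonstrated; it rests on the ceiling accounting for a material part of the missing BC among CI recipients. The rest of the paper and the primary outcomes are unaffected. The correction is worth making because the plot is meant for publication and the remedy is cheap.

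**What to change.** **Protocol.** Align 13.2 and 16 with 6.1.3, so that routinely measured pre-implant thresholds are entered for every newly registered patient. Add a code for thresholds that could not be measured, distinct from those not entered.

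**SAP section 2.**
- Report AC and BC completeness by device type, including the CI denominator.
- Compare age, degree of loss, etiology, device type and centre between records with and without AC/BC.
- Show unmeasurable BC as censored at the limit, and do not drop it.
- Limit conclusions from the SN/CO plot to the subset with data.
- Account for the four records between 165 and 169.

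**Cost.** Wording changes, a little more entry from existing audiograms, and one extra table. No new measurement is asked for. Entering audiograms for patients already registered would help but is optional, and how many values could be recovered is unknown. For existing records, BC can be shown as censored only where the reason for its absence is recorded or can be established.

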6.2 Study End-points

6.2.1 Primary End-points

The intra-subject comparison of baseline and annual post-implant follow-up assessments on the HUI Mark III and SSQ will be used to examine and determine the type and degree of any changes reported on an individual basis longitudinally for all implanted patients.

Inter-subgroup comparison of baseline and post-implant annual assessments on the HUI Mark III and SSQ will be used to determine the type and degree of reported changes between comparable device type and configuration user groups.

Comparisons between device user groups and device configurations will be made for clinically logical subgroups. E.g. Patients of comparable age will be compared across the subgroups.

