4.1 Preclinical testing

No preclinical testing is required for enrolment of an implanted subject into the registry outside of routine clinical practice.

5 Study Objectives

- To evaluate longitudinal subjective benefit data using validated standardised questionnaires (HUI Mark III and SSQ) for prospectively implanted adult and adolescents using unilateral; bilateral or bimodal configurations of device types.
- To provide statistically valid data to support patient management decisions at the clinical, administrative, reimbursement and regulatory levels locally, nationally and internationally.
- To establish benefits and device functionality for bilateral use over unilateral use for scientific, regulatory and market oriented communications

The hypotheses:

The information gathered shall be used to test the primary hypotheses that implantable hearing solutions improve **the auditory performance** of implant recipients compared to their preimplant condition.

Reported benefits evaluated at 1 year postimplant will remain stable at 2nd and 3rd year postimplant compared to the Baseline evaluation of the preimplant condition.

Severe to profound bilaterally impaired adults and adolescents undergoing bilateral implantation will report a higher level of benefits post implant on self-reported scales, the SSQ and HUI Mark III, compared to those reported by comparable groups of patients implanted unilaterally at the first year follow-up.

Participation in the observational study presents no additional risk to the patient as they are implanted with market released devices and there is no additional burden to the subjects beyond clinical followup.

6 Study Design and End-points

The clinical investigation is designed as a prospective repeated measures longitudinal study with intra-subject controls and inter-group comparisons for device type and configurations across multiple implant

centres cross-culturally using a selection of evaluation tools including clinically standard self-assessment scales, threshold measures, product specific and non-standardised questionnaires for the clinician and implant recipient made available through the electronic platform. Participating clinics are encouraged to collect data as per the evaluation plan outlined. Evaluation tools are provided via the electronic platform.

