11.3 Patient Informed Consent

The clinician is responsible for and must obtain written informed consent from each patient or their legal representative, prior to collecting any study data and formally enrolling them in the registry. This must occur after the patient is implanted when the decision for type and device configuration has already been taken independently to their decision to participate. Prior to obtaining their signature, verbal explanation and exchange must be provided to include:

- aims and objectives of study participation
- extent of the subject's involvement in terms of time, test intervals and tasks
- personal data privacy in printed material and electronic records
- their ability to cease their participation at any time during the course of the registry

The clinician is responsible to ensure that:

- all patients give written informed consent prior to enrolment in the registry through signing and dating the Patient Informed Consent form.
- a copy of the patient information sheet and consent form are given to the patient and the study details explained verbally.
- all signed patient informed consents are archived in the clinician's file at the centre/clinic, as per local requirements, and **at least for 5 years** after completion of the registry.

12 Data Reporting and Statistical Analysis

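### The planned bilateral-versus-unilateral comparison uses non-randomised groups, with no confounder control specified beyond device type, configuration and comparable age

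*Protocol*

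**What the plan says.** **Hypothesis and use.** Protocol section 5 predicts that "Severe to profound bilaterally impaired adults and adolescents undergoing bilateral implantation will report a higher level of benefits post implant on self-reported scales", "compared to those reported by comparable groups of patients implanted unilaterally at the first year follow-up". Section 14.2 adds: "Established benefits will be used to support benefit claims from use of bilateral stimulation over unilateral stimulation".

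**Allocation.** There is none. Under section 11.3, consent is taken "when the decision for type and device configuration has already been taken independently to their decision to participate". Section 6 attributes the device decision to patient and clinician.

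**Grouping.** Section 6.2.1 states "Comparisons between device user groups and device configurations will be made for clinically logical subgroups", followed, as an example, by "Patients of comparable age will be compared across the subgroups". Section 6 also groups by device type and configuration and asks for comparable age. It sets a minimum of 100 per subgroup for HUI3 and, ideally, 50 to 100 for SSQ.

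**Method.** Section 6 says SSQ subscale scores will be "compared across time both intra-subject and inter-subject using parametric tests of comparison". HUI3 is to follow the questionnaire developer's procedures. Neither statement names a covariate. The synopsis defines the endpoint as change from baseline. Section 6.2.2 uses the questionnaire and hearing data to describe patient profiles and look for subgroup differences, not to adjust the comparison.

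**SAP.** It contains no bilateral-versus-unilateral test, and its section 1.1 reports that bilateral summaries were not possible because numbers were small. Its introduction leaves any earlier analysis plan in force.

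**The concern.** Bilateral and unilateral recipients may differ at baseline in self-rated hearing, health utility, duration and degree of loss, hearing-aid use, and the country or centre that treated them. If such factors also affect gain, an unadjusted difference mixes them with the effect of the second device.

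The SAP itself treats several of these as possible influences on gain. Section 4.1.2.2 lists etiology, age, duration, onset, hearing-aid use, tinnitus and dizziness, and section 4.1.2.3 adds the baseline HUI3 score. The protocol carries none of them except age into the configuration comparison. At stake is a benefit claim meant for scientific, regulatory and market audiences.

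**Working it through.** **The plan's own figures.** The 100 (HUI3) and 50 to 100 (SSQ) per subgroup cannot be reproduced, because no effect size, SD or power is given for this comparison. For scale, with the SAP's HUI3 change SD of 0.22 and 80% power at two-sided 5%, 100 per group detects (1.96 + 0.84) × 0.22 × √(2/100) = 0.087.

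**Does gain depend on baseline?** SAP section 4.1.2.3, Table 2, cross-tabulates the HUI3 hearing attribute at baseline and visit 1 for 133 patients.
- Baseline category above 3: 86 patients, net 159 levels gained, mean 159/86 = +1.85.
- Baseline category 3 or below: 47 patients, net 20 levels lost, mean −20/47 = −0.43.

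Part of this contrast is regression to the mean on a bounded scale. That mechanism also turns a baseline gap into a difference in change.

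**Size of the effect.** The inputs are the pre, post and paired-difference SDs in SAP section 1.3.1, Table 2. For HUI3 they are 0.188, 0.168 and 0.182.

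1. Pre-post correlation: r = (SDpre² + SDpost² − SDdiff²)/(2 × SDpre × SDpost) = (0.035344 + 0.028224 − 0.033124)/0.063168 = 0.482.
2. Slope of follow-up on baseline: b = r × SDpost/SDpre = 0.482 × 0.168/0.188 = 0.431.
3. False difference in gain = (1 − b) × baseline gap = 0.569 × gap. A gap of 0.05 gives 0.028 and a gap of 0.10 gives 0.057.
4. Gap that produces 0.03 by itself: 0.03/0.569 = 0.053, or 0.28 SD.

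**False-positive rate.** With SE = SDdiff × √(2/n) and false difference d, the two-sided rate is Φ(d/SE − 1.96) + Φ(−d/SE − 1.96). For a HUI3 gap of 0.5 SD (0.094) at n = 100, d = 0.0535, SE = 0.0257, d/SE = 2.08, and the rate is 55%.

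All gaps below are assumed. There is no true device effect, and n = 100 per group:

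| Change in | r | 1 − b | False difference at 0.25 / 0.5 / 0.75 SD | False-positive rate |
|---|---|---|---|---|
| HUI3 | 0.48 | 0.569 | 0.027 / 0.054 / 0.080 | 18% / 55% / 88% |
| SSQ Speech | 0.36 | 0.645 | 0.28 / 0.55 / 0.83 | 17% / 53% / 86% |
| SSQ Spatial | 0.78 | 0.144 | 0.07 / 0.14 / 0.21 | 6% / 11% / 19% |
| SSQ Qualities | 0.67 | 0.141 | 0.05 / 0.10 / 0.14 | 6% / 8% / 12% |

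At 50 per group the HUI3 rates are 11%, 31% and 60%. On the change scale the false difference favours whichever group starts lower.

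**The case against.** Several counter-arguments have force.

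- **Age is an example, not the whole rule.** A reader might infer that groups are matched on age alone. The documents do not support that. No matching is described, device type also defines the groups, and the hypothesis is limited to severe-to-profound loss in both ears and to comparable unilateral recipients. What stands is that *comparable* is never defined and no other patient factor is named in the grouping rules.
- **The data are not ignored.** Baseline scores, thresholds and questionnaire answers are to be compared or described across subgroups. They are simply not used as adjusters.
- **Parametric testing is stated for SSQ only**, not for HUI3.
- **Change scores cancel purely additive differences.** If the groups differ stably and would have changed in parallel, an unadjusted change score is unbiased and adjusting for baseline introduces bias. The choice is contested for non-randomised groups, so the fix should not rely on one analysis.
- **The sizes are modest against other yardsticks.** SAP section 1.3.1 calls 0.03 very small and takes 0.1 as the difference of interest for HUI3. Reaching 0.1 needs a gap of 0.1/0.569 = 0.176, or 0.93 SD. Even a 0.75 SD gap in SSQ Speech gives 0.83, well below the stated 2 units.
- **The comparison may not be run, or may already be adjusted.** The synopsis makes it conditional on numbers, the SAP omits it, and protocol section 12.1 cites a separate analysis proposal that is not available here. Even so, the protocol's hypothesis and intended claim remain, and the SAP does not supersede earlier plans.

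**Conclusion.** The concern holds in a limited form. A non-randomised comparison is meant to support a superiority claim, and neither document specifies confounder control beyond device type, configuration and comparable age. Baseline differences may therefore be mistaken for a device effect. For HUI3 and SSQ Speech, moderate assumed imbalances could push the false-positive rate well above 5%; for SSQ Spatial and Qualities the effect on change scores is small.

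A reader might go further and infer that baseline differences will show up as a bilateral benefit. The documents do not support that. Nothing in them says which group starts lower, and if bilateral recipients start higher the bias runs against the claim.

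The sizes rest on three assumptions: the baseline gaps are hypothetical; the correlations are derived from SAP Table 2, where the pre, post and paired counts differ (29, 38 and 27 for HUI3), and are not stated there; and follow-up given baseline is taken not to depend on group.

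**What to change.** In protocol sections 6 and 6.2.1:

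1. Define *comparable*. Replace the unadjusted between-configuration tests with a regression of outcome on configuration among recipients with severe-to-profound loss in both ears.
2. Adjust for a short pre-specified set already collected: age, duration of loss, hearing-loss degree category, hearing-aid use, and country or centre as a random effect or grouped factor. Use the degree category instead of ear-specific thresholds, because SAP section 2.3.1 reports that most CI records lack specific air- or bone-conduction values. If bilateral numbers cannot support the full set, use a propensity score.
3. Report the analysis adjusted for baseline score and the covariate-adjusted change-score analysis side by side, and say how a disagreement will be interpreted.
4. State that no bilateral superiority claim will rest on unadjusted comparisons and that unmeasured confounding remains.
5. If the separate proposal in section 12.1 already specifies adjustment, cite it in section 6.2.1.

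The cost is protocol and SAP wording, with no new data collection. The downsides are some loss of precision with few bilateral recipients, incomplete covariates in some records, and residual confounding that no adjustment can remove.
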